Table 76: **Time to Death through Day 15 and 29 by Treatment Group and Baseline Ordinal Score – As Treated Population**

Table 77: **Time to Death through Day 15 and 29 by Treatment Group and Baseline Modified Oxygen Use Ordinal Score – mITT Population**

Table 78: **Time to Death through Day 15 and 29 by Treatment Group and Baseline Modified Oxygen Use Ordinal Score – As Treated Population**

Table 79: **Time to Death through Day 15 and 29 by Treatment Group within Subgroups – mITT Population**

Table 80: **Time to Death through Day 15 and 29 by Treatment Group: Medications of Interest Sensitivity Analysis – mITT Population**

Table 81: **Time to Death through Day 15 and 29 by Treatment Group: Interaction Modeling – mITT Population**

Programming notes for Table 77 and Table 78:

The table will include the footnote: This analysis used a modified version of the ordinal scale where the definitions of categories 5 and 6 are, respectively, “Hospitalized, requiring supplemental oxygen or high flow oxygen devices at oxygen flow rate less than or equal to 15L/min” and “Hospitalized, on non-invasive ventilation or high flow oxygen devices at oxygen flow rate greater than 15L/min”.

Programming notes for Table 79:

Log-rank p-values will not be included in this table so the column will be removed. The Baseline Ordinal Score column will be removed and to the left of the Study Day column, a column titled “Analysis/Subgroup” will be inserted. Rows will be generated for each subgroup. This table will include the statin/ARB/AECI use subgroups. Baseline Ordinal Score will be excluded from this table; only subjects with baseline ordinal score of 4 or 5 will be included.

Programming notes for Table 80:

Log-rank p-values will not be included in this table so the column will be removed. The table will include a column to the left of the “n” column titled “m”. The corresponding footnote will read “m = Number of subjects reporting use of the medication of interest.” The Baseline Ordinal Score column will be removed and a “Medication of Interest” column will be inserted to the left of Study Day. Separate models will be fit for the following categories of medications (see Section 6.4):

- Any Medication of Interest

- Hydroxychloroquine/Chloroquine
- Corticosteroids
- Anti-Inflammatory Drugs

Include a footnote for “Any Medication of Interest” noting that this excludes statins, ARBs, and AECIs. The table will include the following footnote: “In this analysis, subjects that reported use of the specified medications of interest (Section 6.4) are censored at time of medication receipt.” Only subjects with baseline ordinal score of 4 or 5 will be included

Programming notes for Table 81:

This table will only include the Treatment Group and HR columns only as well as a column to the left of Treatment Group titled “Interaction”. The following models will be run:

- “Treatment – Baseline Ordinal Score (4 or 5 vs. 6)” will include a treatment*Baseline Ordinal Score interaction term.
- “Treatment – Continuous Actual Baseline Ordinal Score” will include a treatment*baseline ordinal score interaction term.
- “Treatment – Categorical Actual Baseline Ordinal Score” will include a treatment*baseline ordinal score interaction term.

Only run the actual severity models if at least one subject was randomized to the incorrect stratum. For each interaction model, the p-value for the interaction term will be provided in a footnote reading “The p-value for the treatment by [Baseline ordinal score / continuous/categorical baseline ordinal score] interaction term was 0.xxxx.”.

Table 82: Time to Death through Day 15 and 29 by Treatment Group: Restricted Mean Survival Time Analysis – mITT Population

Study Day	Treatment Group	Baseline Ordinal Score	n	Restricted Mean Recovery Time		Difference				
				Estimate	95% CI	Estimate	95% CI			
Day 15	Interferon beta-1a + RDV (N=X)	4	x	x.x	x.x, x.x	x.xx	x.xx, x.xx			
	Placebo + RDV (N=X)		x	x.x	x.x, x.x					
	Interferon beta-1a + RDV (N=X)	5	x	x.x	x.x, x.x	x.xx	x.xx, x.xx			
	Placebo + RDV (N=X)		x	x.x	x.x, x.x					
	Interferon beta-1a + RDV (N=X)	6	x	x.x	x.x, x.x	x.xx	x.xx, x.xx			
	Placebo + RDV (N=X)		x	x.x	x.x, x.x					
	Interferon beta-1a + RDV (N=X)	Any Baseline Ordinal Score	x	x.x	x.x, x.x	x.xx	x.xx, x.xx			
	Placebo + RDV (N=X)		x	x.x	x.x, x.x					
	Interferon beta-1a + RDV (N=X)	Any Baseline Ordinal Score (4 or 5)	x	x.x	x.x, x.x	x.xx	x.xx, x.xx			
	Placebo + RDV (N=X)		x	x.x	x.x, x.x					
Repeat for Day 29										
N= Number of subjects in the specified treatment group, baseline ordinal score, and analysis population.										
n = Number of recovered subjects.										
Difference is the difference in the restricted mean recovery time between Interferon beta-1a + RDV and Placebo + RDV.										

Table 83: Time to Death or Progression to Invasive Ventilation through Day 28 by Treatment Group and Baseline Ordinal Score – mITT Population

Treatment Group	Baseline Ordinal Score	n	HR	
			Estimate	95% CI
Interferon beta-1a + RDV (N=X)	4	x	x.xx	x.xx, x.xx
Placebo + RDV (N=X)		x		
Interferon beta-1a + RDV (N=X)	5	x	x.xx	x.xx, x.xx
Placebo + RDV (N=X)		x		
Interferon beta-1a + RDV (N=X)	6	x	x.xx	x.xx, x.xx
Placebo + RDV (N=X)		x		
Interferon beta-1a + RDV (N=X)	Any Baseline Ordinal Score	x	x.xx	x.xx, x.xx
Placebo + RDV (N=X)		x		
Interferon beta-1a + RDV (N=X)	Any Baseline Ordinal Score (4 or 5)	x	x.xx	x.xx, x.xx
Placebo + RDV (N=X)		x		

NE = Not Estimated.

N= Number of subjects in the specified treatment group, baseline ordinal score, and analysis population.

n = Number of subjects who died or progressed to invasive ventilation by Day 28.

HR is the ratio of the hazard of death or progression to invasive ventilation in each treatment group estimated from the Cox model. The ratio is Interferon beta-1a + RDV to Placebo + RDV.

HR for the ‘Any Baseline Ordinal Score’ and ‘Any Baseline Ordinal Score (4 or 5)’ group is the hazard ratio from the stratified Cox Model.

Tables with similar format:

Table 84: **Time to Death Progression to Invasive Ventilation through Day 28 by Treatment Group and Baseline Ordinal Score – As Treated Population**

Table 85: **Time to Death Progression to Invasive Ventilation through Day 28 by Treatment Group and Baseline Modified Oxygen Use Ordinal Score – As Treated Population**

Table 86: **Time to Death or Progression to Non-Invasive or Invasive Ventilation through Day 28 by Treatment Group and Baseline Modified Oxygen Use Ordinal Score – mITT Population**

Table 87: **Time to Death or Progression to Non-Invasive or Invasive Ventilation through Day 28 by Treatment Group and Baseline Ordinal Score – mITT Population**

Table 88: **Time to Death or Progression to Non-Invasive or Invasive Ventilation through Day 28 by Treatment Group and Baseline Ordinal Score – As Treated Population**

Table 89: **Time to Death or Progression to Non-Invasive or Invasive Ventilation through Day 28 by Treatment Group, Baseline Ordinal Score, and Statin/ARB/AECI Use – mITT Population**

Programming Notes for Table 85 and Table 86:

The table will include the footnote: This analysis used a modified version of the ordinal scale where the definitions of categories 5 and 6 are, respectively, “Hospitalized, requiring supplemental oxygen or high flow oxygen devices at oxygen flow rate less than or equal to 15L/min” and “Hospitalized, on non-invasive ventilation or high flow oxygen devices at oxygen flow rate greater than 15L/min”.

Programming notes for Table 89:

Use the Statins use subgroups described in Section 6.4. The Baseline Ordinal Score column will be replaced by a “Statins Use” column. Only subjects with a baseline score of 4 or 5 will be included.

Table 90: Subjects Experiencing Grade 3 or 4 AEs and SAEs through Day 29 by Treatment Group and Baseline Ordinal Score – As Treated Population

Safety Event Outcome	Interferon beta-1a + RDV			Placebo + RDV		
	n	%	95% CI	n	%	95% CI
Any Baseline Ordinal Score (N = X)						
Grade 3 or 4 AE	x	x	x.x, x.x	x	x	x.x, x.x
SAE	x	x	x.x, x.x	x	x	x.x, x.x
Any Baseline Ordinal Score (4 or 5) (N = X)						
Grade 3 or 4 AE	x	x	x.x, x.x	x	x	x.x, x.x
SAE	x	x	x.x, x.x	x	x	x.x, x.x
Baseline Ordinal Score 4 (N = X)						
Grade 3 or 4 AE	x	x	x.x, x.x	x	x	x.x, x.x
SAE	x	x	x.x, x.x	x	x	x.x, x.x
Baseline Ordinal Score 5 (N = X)						
Grade 3 or 4 AE	x	x	x.x, x.x	x	x	x.x, x.x
SAE	x	x	x.x, x.x	x	x	x.x, x.x
Baseline Ordinal Score 6 (N = X)						
Grade 3 or 4 AE	x	x	x.x, x.x	x	x	x.x, x.x
SAE	x	x	x.x, x.x	x	x	x.x, x.x

N = Number of Subject in the As Treated Population and specified baseline ordinal score stratum.

n = Number of subjects in a given treatment group who experienced the specified safety event outcome.

95% CI calculated using C-P/Blaker method.

Table 91: Analysis of Time to Death, SAEs, or Grade 3 or 4 AEs by Treatment Group – As Treated Population

Baseline Ordinal Score	Treatment Group	n	HR	
			Estimate	95% CI
Any Baseline Ordinal Score (N=X)	Interferon beta-1a + RDV (N=X)	X	X.XX	X.XX, X.XX
	Placebo + RDV (N=X)	X		
Any Baseline Ordinal Score (4 or 5) (N=X)	Interferon beta-1a + RDV (N=X)	X	X.XX	X.XX, X.XX
	Placebo + RDV (N=X)	X		
Baseline Ordinal Score 4 (N=X)	Interferon beta-1a + RDV (N=X)	X	X.XX	X.XX, X.XX
	Placebo + RDV (N=X)	X		
Baseline Ordinal Score 5 (N=X)	Interferon beta-1a + RDV (N=X)	X	X.XX	X.XX, X.XX
	Placebo + RDV (N=X)	X		
Baseline Ordinal Score 6 (N=X)	Interferon beta-1a + RDV (N=X)	X	X.XX	X.XX, X.XX
	Placebo + RDV (N=X)	X		

N= Number of subjects in the As Treated Population and specified baseline ordinal score stratum.
n = Number of subjects who died or experienced SAEs or Grade 3 or 4 AEs.
HR is the ratio of the hazard of Death/SAE/AE of Grade 3 or 4 in each treatment group estimated from the Cox model. The ratio is Interferon beta-1a + RDV to Placebo + RDV.
HR for the 'Any Baseline Ordinal Score' and 'Any Baseline Ordinal Score (4 or 5)' group is the hazard ratio from the stratified Cox Model.

Table 92: Abnormal Laboratory Results of Grade 3 or 4 by Parameter, Maximum Severity, Time Point, and Treatment Group – As Treated Population, Baseline Ordinal Score of 4 or 5

Laboratory Parameter	Time Point	Treatment Group	N	Severe/ Grade 3		Life Threatening/ Grade 4		Severe/Grade 3 or Life Threatening/Grade 4	
				n	%	n	%	n	%
Any Parameter	Baseline	Interferon + RDV	x	x	x	x	x	x	x
		Placebo + RDV	x	x	X	x	x	x	x
	Day 3	Interferon + RDV	x	x	X	x	x	x	x
		Placebo + RDV	x	x	X	x	x	x	x
	Day 5	Interferon + RDV	x	x	X	x	x	x	x
		Placebo + RDV	x	x	X	x	x	x	x
	Day 8	Interferon + RDV	x	x	X	x	x	x	x
		Placebo + RDV	x	x	X	x	x	x	x
	Day 11	Interferon + RDV	x	x	X	x	x	x	x
		Placebo + RDV	x	x	X	x	x	x	x
	Day 15	Interferon + RDV	x	x	X	x	x	x	x
		Placebo + RDV	x	x	X	x	x	x	x
	Day 29	Interferon + RDV	x	x	X	x	x	x	x
		Placebo + RDV	x	x	X	x	x	x	x
	Maximum Severity Post Baseline		Interferon + RDV	x	x	X	x	x	x
			Placebo + RDV	x	x	X	x	x	x

Each parameter will be summarized individually similar to the above...

The “Max Post Baseline” rows indicate the maximum severity experienced by each subject at any time point post baseline, including unscheduled assessments and assessments beyond Day 29.
N = Number of subjects in the As Treated Population

Programming Note: D-dimer and CRP results are not included in this table. Include all lab parameters that are being graded in this table.

Table with similar format:

Table 93: Abnormal Laboratory Results of Grade 3 or 4 by Parameter, Maximum Severity, Time Point, and Treatment Group – As Treated Population, Baseline Ordinal Score of 6

Table 94: Treatment-Emergent Laboratory Abnormalities - As Treated Population, Baseline Ordinal Score of 4 or 5

Laboratory Parameter	Grade	Interferon beta-1a + RDV (N=X)			Placebo + RDV (N=X)		
		N	n	%	N	n	%
Any Parameter	1	x	x	x	x	x	x
	2	x	x	X	x	x	x
	3	x	x	X	x	x	x
	4	x	x	X	x	x	x
	Any Grade	x	x	X	x	x	x

Continue for all graded parameters

N = Number of subjects in the As Treated Population with any post-baseline data available for the specified Lab Parameter.
n = Number of subjects in the As Treated Population with treatment emergent abnormalities for the specified Lab Parameter.
A treatment emergent laboratory abnormality is defined as a post-baseline abnormal value with a severity grade greater than at baseline.

Table with similar format:

Table 95: Treatment-Emergent Laboratory Abnormalities - As Treated Population, Baseline Ordinal Score of 6

Table 96: Summary Statistics of Laboratory Results by Parameter, Study Visit Day, and Treatment Group – As Treated Population, Baseline Ordinal Score of 4 or 5

Laboratory Parameter	Study Visit Day	Treatment Group	Absolute					Change from Baseline				
			N	Mean	95% CI	Median	Min, Max	N	Mean	95% CI	Median	Min, Max
Parameter 1	Baseline	Interferon + RDV	x	xx.x	xx.x, xx.x	xx.x	xx.x, xx.x	---	---	---	---	---
		Placebo + RDV	x	xx.x	xx.x, xx.x	xx.x	xx.x, xx.x	---	---	---	---	---
	Day 3	Interferon + RDV	x	xx.x	xx.x, xx.x	xx.x	xx.x, xx.x	x	xx.x	xx.x, xx.x	xx.x	xx.x, xx.x
		Placebo + RDV	x	xx.x	xx.x, xx.x	xx.x	xx.x, xx.x	x	xx.x	xx.x, xx.x	xx.x	xx.x, xx.x
	Day 5	Interferon + RDV	x	xx.x	xx.x, xx.x	xx.x	xx.x, xx.x	x	xx.x	xx.x, xx.x	xx.x	xx.x, xx.x
		Placebo + RDV	x	xx.x	xx.x, xx.x	xx.x	xx.x, xx.x	x	xx.x	xx.x, xx.x	xx.x	xx.x, xx.x
	Day 8	Interferon + RDV	x	xx.x	xx.x, xx.x	xx.x	xx.x, xx.x	x	xx.x	xx.x, xx.x	xx.x	xx.x, xx.x
		Placebo + RDV	x	xx.x	xx.x, xx.x	xx.x	xx.x, xx.x	x	xx.x	xx.x, xx.x	xx.x	xx.x, xx.x
	Day 11	Interferon + RDV	x	xx.x	xx.x, xx.x	xx.x	xx.x, xx.x	x	xx.x	xx.x, xx.x	xx.x	xx.x, xx.x
		Placebo + RDV	x	xx.x	xx.x, xx.x	xx.x	xx.x, xx.x	x	xx.x	xx.x, xx.x	xx.x	xx.x, xx.x
	Day 15	Interferon + RDV	x	xx.x	xx.x, xx.x	xx.x	xx.x, xx.x	x	xx.x	xx.x, xx.x	xx.x	xx.x, xx.x
		Placebo + RDV	x	xx.x	xx.x, xx.x	xx.x	xx.x, xx.x	x	xx.x	xx.x, xx.x	xx.x	xx.x, xx.x
	Day 29	Interferon + RDV	x	xx.x	xx.x, xx.x	xx.x	xx.x, xx.x	x	xx.x	xx.x, xx.x	xx.x	xx.x, xx.x
		Placebo + RDV	x	xx.x	xx.x, xx.x	xx.x	xx.x, xx.x	x	xx.x	xx.x, xx.x	xx.x	xx.x, xx.x
Continue for all parameters...												
N = Number of subjects in the As Treated Population with laboratory data available for the parameter at the specified study visit.												

Programming Note: Include all lab parameters in this table except d-dimer and CRP.

Table with similar format:

Table 97: Summary Statistics of Laboratory Results by Parameter, Study Visit Day, and Treatment Group – As Treated Population, Baseline Ordinal Score of 6

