3.3.2. Recovery and Time to Recovery

The primary efficacy and one of the key secondary outcome measures is the time to recovery assessed through Day 29 + 6 days. Recovery will be defined as having a value of 1, 2, or 3 on the clinical status 8-point ordinal scale. The time to recovery will be defined as the elapsed time (in days) from randomization to the earliest day at which a subject reaches recovery. Note that since clinical status assessments are recorded as defined in Section 4.3, the day that is being assessed (not necessarily the day the response is collected) will be used to determine the timing of events. For example, a subject with a score of 5 recorded on Days 1-3 and a score of 3 recorded on

Day 4 will have a time to recovery equal to 3 days. It is also possible that a subject has a clinical status score > 3 reported for a particular day but was subsequently discharged on the same day. Such cases and other special cases will be reviewed by the Endpoint Review Committee or the NIAID Medical Officer, or her designee(s), to make the determination of whether the subject should be considered recovered in analyses. Subject data to be reviewed as part of this determination will include the reported clinical status scores while hospitalized, where the subject was discharged to (e.g. private residence, rehabilitation facility, long-term care/nursing home, comfort and care), and any information regarding readmittance. Subjects discharged to hospice or other end-of-life care will not be considered recovered. Additional information may be solicited to assess recovery.

Any subjects that are lost to follow-up or terminated early prior to an observed recovery will be censored at the day of their last observed assessment. Subjects who complete follow-up but do not experience recovery will be censored at the day of their Day 29 visit. All deaths that occur on or before Day 29 (and prior to any observed recovery) will be considered censored at 28 days. Note that we do not expect many subjects to worsen after discharge. However, we will evaluate whether any discharged subjects subsequently experience a worse clinical status and sensitivity analyses will be conducted accordingly. For these analyses, subjects who recover but are later readmitted for COVID-19 will not be considered a recovery but will instead be censored at 28 days.

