8. EFFICACY EVALUATION

8.1. Primary Efficacy Analysis

8.1.1. Primary Analysis of Time to Recovery

The primary analysis uses the stratified log rank test to compare treatment to control through Day 29 with respect to time to recovery, as defined in Section 3.3. Stratification is based on ordinal scale at baseline (4, 5, or 6). As noted in Section 3.3, all deaths within 29 days will be considered censored at Day 29 with respect to time to recovery. Conceptually, a death corresponds to an infinite time to recovery, but censoring at any time greater than or equal to Day 29 gives the same answer as censoring at Day 29; both correspond to giving deaths the worst rank.

As noted in Section 6.6.3, to maintain an overall two-sided type-I error rate of 0.05, the Lan-DeMets spending function analog of the O'Brien-Fleming boundary will be used to derive the cumulative error spending and boundaries for the interim analysis.

For the final analysis, the log rank test will be performed using the pseudocode provided in Section 6.1. The following pseudocode can be used to compute the bounds for the final analyses and compare to the calculated log-rank statistic. The Boundaries dataset will contain the updated boundaries calculated from the interim analyses using the actual information levels observed at the interim analysis.

```

dataParms_LogR;
  set logrankp(rename=(Statistic=Estimate));
  if Variable='TreatmentVariable';
  _Scale_='Score';
  _Stage_=AnalysisNumber;
  keep Variable _Scale_ _Stage_ StdErr Estimate;
run;

proc seqtest Boundary=Boundaries
 Parms (Testvar=TreatmentVariable)=Parms_LogR
  infoadj=prop
  boundaryscale=score
  ;
  ods output Test=FinalResults ParameterEstimates = LogHRest;
run;

```

If the trial is stopped at the interim analysis, then to derive the p-value, hazard ratio estimate, and confidence interval for the early and final analysis sets, stage-wise ordering of the sample space will be used [5]. The resulting p-value, median unbiased estimate, and confidence interval will be presented in the final report. If the trial is not stopped early, then the fixed sample estimates of the statistics using an alpha level of 5% will be computed and reported for the final analysis. The SAS pseudocode above provides estimates for the log hazard ratio and so the estimates will be exponentiated and reported.

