As noted in Section [6.4](#), analyses that take into account concomitant medication will be performed ([Table 14](#)). An additional sensitivity analysis will evaluate the effect of recoveries that were not sustained as indicated in Section [3.3.2](#) ([Table 15](#)).

A restricted mean survival time analysis will be performed as an exploratory analysis. The restricted mean recovery time estimates will be provided for each treatment group and baseline disease severity stratum as well as the difference in restricted mean recovery time between treatment groups within each of the severity strata ([Table 16](#)).

In addition, a forest plot will be generated for the “leave one out” sensitivity analyses described in Section [6.7](#) ([Figure 10](#)); hazard ratio estimates and CIs will be provided for each subgroup that leaves a single site out.

Two corroborative summaries will also be generated. A summary of the number and percentage of subjects in each treatment group who recovered (and are alive), did not recover (and are alive), and died by Day 29 will be summarized. The summary will also include the numbers and percentages, grouping deaths and non-recoveries together ([Table 17](#)). The summaries will also be provided by the Modified Oxygen Use ordinal scale and the duration of symptoms categorizations specified in Section [6.4](#).

Other censoring techniques and additional analyses of the primary outcome may be performed.

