These tables are restricted to subjects with a baseline ordinal score of 4 or 5. P-values will not be included in these tables.

Table 14 will include a column to the left of the “n” column titled “m”. The corresponding footnote will read “m = Number of subjects readmitted for COVID-19.” Table will include the following footnote: “In this analysis, subjects that recover and are subsequently readmitted for COVID-19 are censored at 28 days”.

Table 15 will include a column to the left of the “n” column titled “m”. The corresponding footnote will read “m = Number of subjects reporting use of a medication of interest.” The “Analysis Population” column will be replaced by a column labeled “Medication of Interest”. Separate models will be fit for the following categories of medications (see Section 6.4):

- Any Medication of Interest
- Hydroxychloroquine/Chloroquine
- Corticosteroids
- Anti-Inflammatory Drugs

Include a footnote for “Any Medication of Interest” noting that this excludes statins, ARBs, and AECIs. The table will include the following footnote: “In this analysis, subjects that reported use of the specified medications of interest are censored at time of medication receipt.”

Table 16: Time to Recovery by Treatment Group and Baseline Ordinal Score: Restricted Mean Survival Time Analysis

Analysis Population	Treatment Group	Baseline Ordinal Score	n	Restricted Mean Recovery Time		Difference				
				Estimate	95% CI	Estimate	95% CI			
mITT Population	Interferon beta-1a + RDV (N=X)	4	x	x.x	x.x, x.x	x.xx	x.xx, x.xx			
	Placebo + RDV (N=X)		x	x.x	x.x, x.x					
	Interferon beta-1a + RDV (N=X)	5	x	x.x	x.x, x.x	x.xx	x.xx, x.xx			
	Placebo + RDV (N=X)		x	x.x	x.x, x.x					
	Interferon beta-1a + RDV (N=X)	6	x	x.x	x.x, x.x	x.xx	x.xx, x.xx			
	Placebo + RDV (N=X)		x	x.x	x.x, x.x					
	Interferon beta-1a + RDV (N=X)	Any Baseline Ordinal Score	x	x.x	x.x, x.x	x.xx	x.xx, x.xx			
	Placebo + RDV (N=X)		x	x.x	x.x, x.x					
	Interferon beta-1a + RDV (N=X)	Any Baseline Ordinal Score (4 or 5)	x	x.x	x.x, x.x	x.xx	x.xx, x.xx			
	Placebo + RDV (N=X)		x	x.x	x.x, x.x					
Repeat for the As Treated Population.										
N= Number of subjects in the specified treatment group, baseline ordinal score, and analysis population.										
n = Number of recovered subjects.										
Difference is the difference in the restricted mean recovery time between Interferon beta-1a + RDV and Placebo + RDV.										

Programming Notes:

Within an OS stratum:

```

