proc lifetest data=enrevent plots=(rmst) method=breslow rmst(cl);
by stratum;
time evntday * Censor(1);
strata trtcode /diff=all;
ods output rmst=rmst;
run;
```

Stratified by Baseline Ordinal Score (“Any Baseline Ordinal Score” row).

```
proc lifetest data=enrevent plots=(rmst) method=breslow rmst(cl);
time evntday * Censor(1);
strata trtcode CRSEVERE /diff=all;
ods output rmst=rmst;
run;
```

Table 17: Summary of Recoveries and Deaths by Day 29 – mITT Population

Grouping Variable	Baseline Ordinal Score	Treatment Group	Recovered		Did Not Recover		Deaths		Not Recovered or Died		
			n	%	n	%	n	%	n	%	
Baseline Ordinal Score	4	Interferon beta-1a + RDV (N=X)	x	x	x	x	x	x	x	x	
		Placebo + RDV (N=X)	x	x	x	x	x	x	x	x	
	5	Interferon beta-1a + RDV (N=X)	x	x	x	x	x	x	x	x	
		Placebo + RDV (N=X)	x	x	x	x	x	x	x	x	
	6	Interferon beta-1a + RDV (N=X)	x	x	x	x	x	x	x	x	
		Placebo + RDV (N=X)	x	x	x	x	x	x	x	x	
	Any Baseline Ordinal Score	Interferon beta-1a + RDV (N=X)	x	x	x	x	x	x	x	x	
		Placebo + RDV (N=X)	x	x	x	x	x	x	x	x	
	Any Baseline Ordinal Score (4 or 5)	Interferon beta-1a + RDV (N=X)	x	x	x	x	x	x	x	x	
		Placebo + RDV (N=X)	x	x	x	x	x	x	x	x	
Repeat for Modified Oxygen Use ordinal scale (Section 4.3) and duration of symptoms categories in Section 6.4											
N= Number of subjects in the mITT Population.											

Programming Note: For the categories of “Recovered”, “Did Not Recover” and “Deaths”, subjects who recover but subsequently die will be classified under “Recovered” and “Deaths”. If there are cases of this, a footnote will be added that states “Counts of recoveries and deaths include X subjects who recovered but subsequently died.”

Table 18: Odds Ratio for Better (Lower) Clinical Status Score at Study Visit Day 15 by Treatment Using a Proportional Odds Model, Interferon beta-1a + RDV Relative to Placebo + RDV – mITT Population

Analysis/Subgroup	Treatment Group	Odds Ratio		P-value
		Estimate	95% CI	
Main Analysis of Key Secondary Endpoint				
Analysis of Key Secondary Endpoint ^a	Interferon beta-1a + RDV (N=X)	x.xx	x.xx, x.xx	0.xxx
	Placebo + RDV (N=X)			
Analysis of Key Secondary Endpoint using Modified Oxygen Use Scale				
Analysis of Key Secondary Endpoint ^b	Interferon beta-1a + RDV (N=X)	x.xx	x.xx, x.xx	--
	Placebo + RDV (N=X)			
Subgroup Analyses of Key Secondary Endpoint^c				
[Repeat for each Section 6.4 subgroups]	Interferon beta-1a + RDV (N=X)	x.xx	x.xx, x.xx	--
	Placebo + RDV (N=X)			
Medications of Interest Subgroup Analyses^c				

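### In the exploratory RMST analysis of time to recovery (SAP Table 16), the code for the Any Baseline Ordinal Score row yields no stratified arm difference, and neither program sets a restriction time

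*SAP*

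**What the plan says.** SAP 8.1.2 plans an exploratory RMST analysis of time to recovery. It asks for estimates by arm and baseline severity stratum, and for the "difference in restricted mean recovery time between treatment groups within each of the severity strata". It names no horizon.

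The Table 16 shell (SAP Appendix 1) goes further. Besides rows for baseline scores 4, 5 and 6 it has an Any Baseline Ordinal Score row and a further row for 4 or 5 combined. Each has one RMST per arm and one difference with a 95% CI. Its footnote reads "Difference is the difference in the restricted mean recovery time between Interferon beta-1a + RDV and Placebo + RDV".

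Two programs follow the shell. Both open with "proc lifetest data=enrevent plots=(rmst) method=breslow rmst(cl" and a closing bracket, with no restriction time.
- The first runs BY stratum and uses "strata trtcode /diff=all".
- The second, headed "Stratified by Baseline Ordinal Score" and assigned to the Any row, has no BY statement and uses "strata trtcode CRSEVERE /diff=all".

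SAP 3.3.2 assesses recovery through Day 29 + 6 days and censors deaths before recovery at 28 days. On survivors it says "Subjects who complete follow-up but do not experience recovery will be censored at the day of their Day 29 visit".

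**The concern.** In the first program the variable on the STRATA statement is the compared factor, and severity is handled by BY. The second program moves severity into the same list, where it becomes part of the definition of the compared groups. The heading promises a stratified result, but the code has nothing that separates the stratifier from the arm. SAP 6.1 keeps these roles apart for the log-rank test, with the stratum variable on STRATA and treatment on TEST.

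The missing restriction time is a separate gap. An RMST difference is defined only at a stated horizon. Without one the horizon is taken from the data, and the last few days of follow-up are unusual: deaths stop being counted as unrecovered after day 28, while some survivors are still observed.

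At stake are the pooled RMST rows and the size of every RMST difference in Table 16. No confirmatory result is involved.

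**Working it through.** The documents attach no number to this point, so there is no planned figure to reproduce.

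**Contrasts from the second program.** Inputs: two arms (protocol Appendix C, Study Intervention) and three severity levels (SAP 8.1.1: "Stratification is based on ordinal scale at baseline (4, 5, or 6").
- Groups: 2 × 3 = 6. Pairwise contrasts: 6 × 5 / 2 = 15. Three compare the arms within one severity level; the other 12 compare groups at different levels. None is an overall or stratified arm contrast.
- The SAP does not define CRSEVERE, and the first program uses another name, stratum. If CRSEVERE had two levels: 2 × 2 = 4 groups, 4 × 3 / 2 = 6 contrasts, two of them within severity, and again no stratified contrast.

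This rests on PROC LIFETEST cross-classifying several variables in a STRATA list. The documents do not explain that, but the first program's use of the statement is consistent with it.

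**Sensitivity to the horizon.** Day 29 is 28 days after Day 1, and a visit six days late falls at 28 + 6 = 34 elapsed days. SAP Section 5 supplies the recovery rate ratio of 1.25 and about 90% recovery within 28 days. Curve shapes, death rates and medians below are my assumptions.

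1. *Exponential, 90% recovered at day 28 averaged over arms.* RMST(τ) = (1 − exp(−λτ))/λ, with λ = 0.0742 per day on placebo and 1.25 × 0.0742 = 0.0927 on interferon.

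| τ (days) | Placebo | Interferon | Difference |
|---|---|---|---|
| 14 | 8.71 | 7.84 | −0.87 |
| 21 | 10.64 | 9.25 | −1.40 |
| 28 | 11.79 | 9.98 | −1.81 |
| 34 | 12.40 | 10.33 | −2.07 |

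From 28 to 34 days: (2.07 − 1.81)/1.81 = 14%.

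2. *Weibull, control median 5, 7 or 9 days, 12% of controls unrecovered at day 28, ratio 1.25.* The 28-day difference is 1.81 to 1.88 days and the area added by day 34 is 0.26 to 0.27 day, about 14%.

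3. *Curve flat after day 28, same median range and 12%.* Added area: 6 × (0.12 − 0.12^1.25) = 6 × (0.12 − 0.0706) = 0.30 day. Assumed control/treated 28-day RMSTs of 8.45/6.87, 10.22/8.57 and 11.82/10.14 give differences of 1.58, 1.65 and 1.68 days. The increase is 0.30/1.68 = 18% to 0.30/1.58 = 19%. The no-recovery tail and the assumed shape before day 28 make this the top of the range.

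4. *Simulated Kaplan-Meier curves under the SAP censoring rules* (deaths censored at day 28, survivors at days 28-34, ratio 1.25).
 - 5% deaths: −1.64 days at 28, −1.88 at 34; 0.24/1.64 = 15%. Recovery by day 28 was 84-89%.
 - 15% deaths: −1.48 and −1.72; 0.24/1.48 = 16%. Recovery was 75-79%. The interferon curve fell from 0.207 to 0.116 unrecovered in those six days, partly because the deaths had left the risk set.

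**Sensitivity to the weights.** Assume stratum shares of 15%, 75% and 10% for scores 4, 5 and 6, and 28-day differences of −0.99, −1.56 and +1.65 days.
- Size-weighted: 0.15 × (−0.99) + 0.75 × (−1.56) + 0.10 × 1.65 = −1.15.
- Equal weights: (−0.99 − 1.56 + 1.65)/3 = −0.30.
- Inverse-variance weights (total 923): −1.23.

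The sign in stratum 6 is assumed, to show that the weights have to be stated.

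**The case against.** A reader might infer that the RMST analysis cannot be produced at all, that it is the only summary of the primary outcome free of proportional hazards, and that the analyst must improvise after unblinding. The documents support none of these.
- SAP 8.1.2 asks only for within-stratum differences, and the first program delivers the contrasts for rows 4, 5 and 6. The pooled difference is required by the table shell and the program heading, not by the body text.
- Kaplan-Meier curves, recovery-time quartiles with CIs (Table 10) and counts of recoveries and deaths by Day 29 (Table 17) also avoid proportional hazards.
- The code is a programming note that can be corrected before database lock, and the SAP Preface requires deviations to be described and justified. The analysis is exploratory, and SAP 6.8 gives it no p-value or gatekeeping role.

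On the horizon, SAP 8.1.1 compares the arms through Day 29 and the at-risk counts end there, so 28 elapsed days may be what was meant. But SAP 3.2 and 3.3.2 extend recovery to Day 29 + 6, and nothing carries a horizon into the code. The mortality RMST (Table 82) does name Day 15 and Day 29. How the software would choose the horizon, and whether it would differ between strata, is not described in the documents, so I do not rely on it.

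It is also fair that no weighting scheme appears in the SAP, so any particular one is a preference. What stands is that the Any program does not match its row, the 4-or-5 row has no program, and no horizon is set.

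**Conclusion.** The point holds, as a small correction. The Any program compares arm-by-severity groups and cannot fill its row, however many levels CRSEVERE has; the counts of six and 15 do depend on that undefined variable having levels 4, 5 and 6. For the within-stratum rows the only defect is the unset horizon. Moving it from 28 to 34 days enlarges the difference by roughly 14-19% at a fixed ratio of 1.25. That range is illustrative: it depends on the assumed curve shapes, and 34 days is the latest in-window visit. Nothing here touches the primary stratified log-rank test, alpha or sample size.

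**What to change.** - State a restriction time of 28 days, matching the day at which deaths are censored, in SAP 8.1.2 and in both Table 16 programs.
- Define CRSEVERE and reconcile it with the variable named stratum in the first program.
- Replace the Any program with a pre-stated weighted combination of the within-stratum differences, for example weights w_s = N_s/N with SE = sqrt(Σ w_s² SE_s²). Use the same rule, over strata 4 and 5, for the 4-or-5 row. Another scheme would serve if it is stated in advance.

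The cost is a few lines of text and code in the SAP. No new data are needed, and no other planned analysis changes.
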